Multicenter double-blind placebo-controlled randomized parallel group clinical study of efficacy and safety of MMH-MAP in the treatment of cognitive disorders in patients with ischemic stroke in the carotid arteries

Phase III

Sponsor

OOO «NPF «MATERIA MEDICA HOLDING»

Protocol number Version date:

ClinicalTrials.gov Id:

MMH-MAP-002 June 11, 2019 NCT04295681

Protocol Summary

This document represents the protocol summary for the study on human subjects. The study will be carried out in accordance with ICH GCP, National Standard of the Russian Federation GOST 52379-2005 "Good Clinical Practice", World Medical Association Declaration of Helsinki, relevant requirements of the regulatory authorities as well as the study procedures.

Title of Study

Multicenter double-blind placebo-controlled randomized parallel group clinical study of efficacy and safety of MMH-MAP in the treatment of cognitive disorders in patients with ischemic stroke in the carotid arteries.

Phase: III

Sponsor: Company «MATERIA MEDICA HOLDING», Moscow, Russia *Protocol No.* MMH-MAP-002

Purposes of the study

- To evaluate efficacy of MMH-MAP in the treatment of cognitive disorders in patients with ischemic stroke in the carotid arteries.
- To evaluate the safety of MMH-MAP in the treatment of cognitive disorders in patients with ischemic stroke in the carotid arteries.

Endpoints

Primary endpoint

1. Average MoCA score on treatment day 90.

Secondary endpoints

- 1. Changes in NIHSS score on treatment day 12, 90.
- 2. Percentage of patients with no major disability (mRs 0-1) after 90-day therapy.
- 3. Therapeutic and adverse effects, efficacy index according to clinical global impression scale (CGI-EI) after 90-day therapy.

Safety assessment

- Percentage of patients with sequelae of cerebral infarction (severe infections hospitalacquired pneumonia, uroinfection; deep venous thrombosis, PATE; epileptic episodes) during IMP therapy.
- Frequency of all-cause mortality outcomes during IMP therapy.
- Percentage of patients with recurring cerebral infarction during IMP therapy.
- Occurrence and nature of adverse events (AEs) during the treatment, their intensity (severity), relation to the study drug, outcome.

- Changes in vital signs during IMP therapy.
- Percentage of patients with clinically relevant abnormal laboratory tests during IMP therapy.

Study design

Design: double-blind, randomized, parallel group placebo-controlled clinical study of efficacy and safety of MMH-MAP in the treatment of cognitive disorders in patients with ischemic stroke in the carotid arteries.

The study will enroll hospitalized subjects of either gender aged 40-75 years old with verified diagnosis of ischemic stroke in the carotid arteries within 72 hours post debut having moderate cognitive disorders, moderate neurological deficit.

At Visit 1 (day 1) the subject's complaints and medical history will be collected, objective examination, safety laboratory tests (hematology, serum chemistry, urinalysis) will be performed. The investigator will evaluate the patient's level of consciousness using The Glasgow Coma Scale, intensity of cognitive disorders using The Montreal Cognitive Assessment (MoCA), condition using National Institute of Health Stroke Scale (NIHSS) and The Modified Rankin Scale (mRs). Concomitant therapy will be recorded and changes in cerebral CT/MRI will be evaluated. If the subject meets inclusion criteria and has no exclusion criteria, he/she will be randomized to MMH-MAP or Placebo group. The first dose of the study product should be taken within 72 hours post stroke debut.

At Visit 2 (day 12±3, end of hospitalization period - the last day of hospitalization due to the current stroke) complaints will be collected, objective examination findings will be recorded, monitoring of the prescribed and concomitant therapy will be performed, treatment safety, compliance and stroke severity according to NIHSS will be evaluated.

By the end of hospital therapy the subject will be switched to outpatient therapy with continuation of IMP and medical assistance designed for the treatment of stroke and its sequelae. At Visit 3 (day 45±7 days) the investigator will make a phone call to the subject evaluating the treatment safety.

At final Visit 4 (day 90±7 days) complaints will be collected, objective examination findings will be recorded, monitoring of the prescribed and concomitant therapy will be performed, treatment safety, compliance, condition according to NIHSS will be evaluated, mRs, Clinical Global Impression Efficacy Index (CGI-EI) will be filled. The investigator will perform MoCA testing. Safety laboratory tests (hematology, serum chemistry, urinalysis) will be carried out.

Throughout the study the patient will receive the treatment approved by the decree of the RF Ministry of Health dated 29.12.2012 No. 740n "On approval of standard of special care in

cerebral infarction" except for the products specified in section "Forbidden concomitant therapy".

Inclusion and exclusion criteria

Inclusion criteria

- 1. Age between 40 and 75 years old inclusively.
- 2. Ischemic stroke in the carotid arteries (I 63) within 72 hours post debut.
- 3. Moderate cognitive disorders (MoCA < 26).
- 4. Normal consciousness (Glasgow score 15).
- 5. Stroke severity 8-12 according to NIHSS.
- 6. Disability mRs score 2-3.
- 7. Availability of cerebral CT/MRI within 72 hours post stroke debut.
- 8. Patients who agreed to use a reliable method of contraception during the study.
- 9. Patients who have signed the Participant Information Sheet and Informed Consent.

Exclusion criteria

- 1. Current or previous subarachnoidal/parenchymatous/ventricular hemorrhage, cerebral infarction, cerebral tumour.
- 2. Cerebral CT/MRI findings suggesting cerebral hemorrhage, tumour within 72 hours post stroke debut.
- 3. Scheduled or completed thrombolytic therapy for the treatment of the current cerebral infarction.
- 4. Central nervous system (CNS) diseases including:
 - Inflammatory diseases of the central nervous system (G00-G09);
 - Systemic atrophies primarily affecting the central nervous system (G10-G13);
 - Extrapyramidal and movement disorders (G20-G26);
 - Other degenerative diseases of the nervous system (G30-G32);
 - Demyelinating diseases of the CNS (G35-G37);
 - Episodic and paroxysmal disorders (G40-G47);
 - Polyneuropathies and other disorders of the peripheral nervous system (G60-64), with marked movement and/or sensory impairments that cause movement disorders;
 - Hydrocephalus (G91).
- 5. Head injuries (S00-S09) (including history), accompanied by impaired consciousness, brain contusion or open craniocerebral injuries.
- 6. Musculoskeletal disorders causing motor disturbances.
- 7. Presence (including history) (F00-F03).

- 8. Malignant neoplasms.
- 9. Patients previously diagnosed with class IV heart failure (1964 New York Heart Association functional classification), hypothyroidism, or poorly treated diabetes mellitus.
- 10. Patients having unstable angina or myocardial infarction in the past 6 months.
- 11. Allergy/ intolerance to any of the components of medications used in the treatment.
- 12. Malabsorption syndrome, including congenital or acquired lactase deficiency (or any other disaccharidase deficiency) and galactosemia.
- 13. Any conditions which, according to the investigator opinion, may interfere with the subject's participation in the study.
- 14. Prior history of non-adherence to a drug regimen, a psychiatric disorder, alcoholism or drug abuse, which, in the opinion of the investigator, can compromise compliance with study protocol.
- 15. Pregnancy, breast-feeding; childbirth less than 3 months prior to the inclusion in the trial, unwillingness to use contraceptive methods during the trial.
- 16. Participation in other clinical studies within 3 month prior to enrollment in the study.
- 17. Patients who are related to any of the on-site research personnel directly involved in the conduct of the trial or are an immediate relative of the study investigator. 'Immediate relative' means husband, wife, parent, son, daughter, brother, or sister (regardless of whether they are natural or adopted).
- 18. Patients who work for OOO "NPF "Materia Medica Holding" (i.e. the company's employees, temporary contract workers, designated officials responsible for carrying out the research or any immediate relatives of the aforementioned).

Criteria for Withdrawal or Termination

- 1. Screening failure.
- 2. Inability or patient's refusal to comply with the protocol requirements.
- 3. Necessity in medications prohibited within the study.
- 4. An adverse event requiring discontinuation of the study drug.
- 5. Eligibility error.
- 6. Patient's desire to complete the study early for any reason.
- 7. Pregnancy.
- 8. Participation in any other clinical trial.
- 9. Cases not covered by the protocol where the investigator believes that the patient's continued participation in the study is harmful to him.

Number of subjects

It is planned to include 246 subjects, which is expected to yield at least 196 patients (98 x 2 groups - MMH-MAP and Placebo) completing all protocol procedures.

Interim analysis

The study included two interim analyses: on 15 and 30 percent of the recruited patients. Distribution of the first type error in accordance with the O'Brien–Fleming error waste function, of the second type – in accordance with the Pocock function. It is possible to stop the study early due to both acceptance and rejection of the null hypothesis. The interim analysis is based on the data obtained from the results of examination and treatment of the number of patients established by the protocol who completely completed participation in the study. Number of patients for the first interim analysis: 30 patients (MMN-MAP group - 15 patients, Placebo group - 15 patients). Number of patients for the second interim analysis: 60 patients (MMN-MAP group - 30 patients, Placebo group - 30 patients). Number of patients for the final analysis: 196 patients (MMN-MAP group - 98 patients, Placebo group - 98 patients).

Treatment

Group 1

Name of the medicinal product: MMH-MAP

Active ingredient: Modified affinity purified antibodies to S100 brain-specific protein - 0.006 g*.

* applied onto lactose monohydrate as a water-alcohol mixture containing no more than 10^{-391} ng/g active form of the API

Excipients: Lactose monohydrate - 0.267 g

Microcrystalline cellulose - 0.030 g

Magnesium stearate - 0.003 g

Method of administration: Tablet for oral use. 2 tablets twice daily (approximately at the same time), outside the meal (between meals or 15 minutes before meals or fluids). Keep the tablets in mouth until completely dissolved.

Dosage form: Tablets.

Description: Flat cylinder-shaped scored beveled edge white to off-white tablets with a smooth, uniform surface.

Storage conditions: At temperature ≤ 25 °C.

Group 2

Name of the medicinal product: Placebo

Active ingredient: No

Excipients: Lactose monohydrate - 0.267 g

Microcrystalline cellulose - 0.030 g Magnesium stearate - 0.003 g

Method of administration: Tablet for oral use. Dose per administration: 2 tablets. 2 tablets twice daily (4 tablets/day). The tablets should be held in mouth without chewing until complete dissolution.

Dosage form: Tablets.

Description: Flat cylinder-shaped scored beveled edge white to off-white tablets with a smooth, uniform surface.

Storage conditions: Store at a temperature not exceeding 25 ° C.

Treatment duration

MMH-MAP/Placebo treatment duration is 90 days.

Observation period

In total the patients will be monitored for 90 days.

Hospital stage - 12 days;

Outpatient stage – 78 days.

Symptomatic (Standard) treatment

During the study, patients can receive basic therapy approved by order No. 1740n of the Ministry of Health of the Russian Federation dated December 29, 2012 "On approval of the standard of specialized care for cerebral infarction."

Basic therapy is selected for each patient individually and may include: antihypertensive drugs, ACE inhibitors, angiotensin II receptor antagonists, β -blockers or α - and β -blockers, calcium

antagonists, diuretics (thiazide, aldosterone receptor antagonist), antiplatelet agents

(acetylsalicylic acid, clopidogrel, dipyridamole, ticlopidine, etc.), statins and their combinations, as well as a complex of rehabilitation measures.

Patients are allowed to receive medications used to treat concurrent diseases except for the products listed in section "Forbidden concomitant therapy".

During the study, the patient may receive therapy for concomitant diseases and conditions, except for the medicines specified in the section "Prohibited concomitant treatment."

Prohibited concomitant therapy

During the study (after signing patient information sheet and informed consent form) the following medications are prohibited (ATC group is specified in brackets):

 Nicotinic acid and its derivatives; purines (xanthinol nicotinate, pentoxifylline), ergot alkaloids (nicergoline, alpha-dihydroergocryptine+caffeine), other vasodilators (vincamine, bencyclan, naftidrofuryl), papaverine, etamivan+etophylline+hexobendine.

- 2. Antiepileptic agents (N03A).
- 3. Anchicnolonergic agents (N04A).
- 4. Dopaminergic agents (N04B).
- 5. Actovegin.
- 6. Pyrrolidine derivatives (racetams: piracetam, etiracetam, aniracetam, etc.); idebenone; pyridoxine derivatives (pyritinol, biotredin, etc.); dimethylaminoethanol derivatives (acetylcholine precursors: deanol aceglumate, meclofenoxate etc.).
- 7. Other anti-dementia agents (N06DX): ginkgo biloba, memantine, etc.
- 8. General restoraive agents and adaptogens (A13A): ginseng, melatonin, etc.
- 9. Any unregistered medicinal product and/or vaccine.
- 10. Drugs that previously caused allergic reactions in patient.

Study design scheme

Schedule of study procedures

Procedure/Visit	Visit 1 Screening, Randomization (Day 1)	Visit 2* (Day 12±3 days)	Visit 3 «phone visit» (Day 45±3 days)	Visit 4** (Day 90±7 days)
Informed consent	+			
Registration patient in IVRS and assignment	+			
of a personal code				
Collection of complaints	+	+	+	+
Medical history	+			
Concomitant conditions and diseases	+			

Physical examination	+	+		+
Evaluation of vital				
signs (HR, RR, BP) ***	+	+		+
Recording therapy for				
concomitant diseases	+	+	+	+
Filling MoCA scale	+			+
Filling Glasgow scale	+			
Filling NIHSS scale	+	+		+
Filling mRs scale	+			+
Pregnancy test	+			
Safety laboratory tests	+			+
Inclusion/exclusion	+			
criteria				
Randomization	+			
Dispensing of study	+	+		
drug				
Study drug				
accountability and		+		+
return				
Treatment compliance		+		+
Evaluation of study	Ŧ	Ŧ	Т	–
treatment safety	т	Ŧ	Ŧ	т
Filling CGI-EI scale				+
Visit completion	+	+	+	+
Study completion				+

* The end of the inpatient period is the last day of hospitalization for the current stroke

** Study completion

**** HR - heart rate; RR - respiration rate; BP - blood pressure

Statistical Analyses

Samples

Total set includes all the subjects who have signed ICF. This sample will consider all adverse events (AEs) throughout the study, including those occurred prior to the study therapy.

The sample including all patients who received at least one dose of the study drug to be used for *analysis of the study treatment safety and tolerability* (*Safety population*), as all AEs identified after the study drug administration will be recorded.

Full Analysis Set This sample will consist of all enrolled patients, except for those who met at least one of the following criteria:

- 1) non-compliance with inclusion/exclusion criteria;
- 2) patient did not take any dose of study drug;
- 3) absence of any patient data after administration of study drug.

This was the best set for the Intention-to-treat method, so it will be used in the Intention-to-treat

efficacy analysis (ITT-analysis) of the study therapy.

Per Protocol set. This sample includes all patients who received full protocol therapy and completed all scheduled visits. This set will be used for *Per Protocol analysis (PP analysis) of efficacy of study therapy. Per Protocol set* will not include the patients whose data are fully or partially invalid for analysis due to a protocol deviation.

Protocol deviations resulting in full or partial data invalidity:

- 1. Violation of visit schedule.
- 2. Inappropriate distribution/issue of the study drug.
- 3. Prescription of prohibited therapy.
- 4. Increase or decrease of 25% or more in the amount of study therapy received.
- 5. Inability to assess patient's objective compliance (adherence to therapy) according to the formula (e.g. loss of packaging).
- 6. Gross inconsistencies between source documents and CRF detected during monitoring or other authorized inspection.
- 7. Violations of the Informed consent procedure.
- 8. Non-compliance with the clinical study protocol procedures.
- 9. Inability to collect all patient's data used for evaluation of the study endpoints (e.g. lack of entries in source documents required for verification of inclusion/exclusion criteria, safety and efficacy criteria).
- 10. Other protocol deviations resulting in full or partial data invalidity.

Data treatment and all statistical calculations under the protocol will be made using SAS-9.4 statistical software.¹

Evaluation of sample size

The sample size was assessed in accordance with the following rules and assumptions:

- 1. Statistical assumptions:
 - 1.1 the power of statistical tests 'P = (1β) ' is 80% (the probability of correct rejection of the null hypothesis is 0.8)
 - 1.2 the probability of type 1 error 'a' is less that 5% (the probability of false acceptance of the alternative hypothesis is less than 0.05)
 - 1.3 statistical criteria of intergroup comparisons are two-sided, unless otherwise stated
 - 1.4 calculation of sample size will be based on the assumptions on the expected effect declared in the primary efficacy criterion of the protocol

¹ Holder of license: OOO "NPF "Materia Medica Holding", No. 70100045.

Protocol No. MMH-MAP-002 11-Jun-2019

- 1.5 ratio between sample sizes of MMH-MAP and Placebo sample sizes is 1:1 (1 MMH-MAP patient per 1 Placebo patient)
- 1.6 statistical hypotheses null and alternative hypotheses on the difference between study drug and placebo under the dosing regimen used:

H₀: $\mu_1 - \mu_2 = 0$ H_a: $\mu_1 - \mu_2 \neq 0$

where μ_1 - change in mean MoCA summary score in MMH-MAP group, μ_2 - change in mean MoCA summary score in Placebo group

1.7 calculation of sample size for statistical criteria was made using the following program code:

Proc seqdesign errspend Design nstages = 3 Info = cum (0.15,0.3,1) Method (alpha) = UNI (rho = 0.5 tau = 0) Method (beta) = UNI (rho = 0 tau = 0) Stop = both Alpha = 0.05 Beta = 0.2 Samplesize model = twosamplemean (meandiff = 1.3 stddev = 3.0) Run

1.8 terminal sample size will be determined using the formula:

$$N_T = N_{PP}/(1 - K_{\rm B})$$

where N_T – terminal sample size; N_{PP} – result of calculation in c. 1.7 i.e. scheduled number of patients completing the study per protocol; K_B – withdrawal rate.

2. Assumptions on expected clinical study effects.

It is assumed that the difference between the changes in the mean total MoCA score in the Study Drug and Placebo groups on Day 90 of treatment will be at least 1.3 points with a standard deviation of at least 3.0 points.

Therefore, group size needed to compare Study Drug and Placebo will be **98** patients for each group. Given potential withdrawal of at least 20% patients ($K_B = 0.2$) during the study for various reasons, at least **246** patients will be required to sign informed consent, with **123** patients per group (see cl. 1.8).

Statistical criteria

All statistical calculations will be made using two groups of statistical criteria:

- parametric to obtain effective estimates for random parameters in case the relevant conditions of method/model applicability are not violated (e.g. sphericity, normality, risk proportionality, etc.)
- nonparametric in all other cases.

Parametric criteria

The application of parametric criteria will be accompanied by a check of models for applicability (e.g. Kolmogorov-Smirnov test, Shapiro-Wilk test).

The following parametric methods and approaches are supposed to be used:

- To evaluate the differences in continuous variables obtained in one group at two different visits – Student t-test for paired samples.
- 2. To evaluate time changes in parameters compared analysis of variance (ANOVA) or covariance (ANCOVA) modified with repeated measures.
- 3. In case of multiple comparisons of the groups various corrections for multiplicity will be used, e.g. Dunnett, Tukey, Scheffe, Holm adapted test, etc.
- 4. Generalized Linear Models and/or Mixed Linear Models will be used in case of abnormal data distribution.
- 5. Selection of the type of distribution, specification of factor and covariance structures of the model will be made using fit-statistics such as AIC (Akaike information criterion).

The following SAS software programs are supposed to be applied to the above listed tests and techniques:

- UNIVARIATE normality verification of the distributions under comparison
- CORR, MEANS calculation of descriptive statistics
- TTEST Student's test with all modifications
- GLM generalized linear models for studying temporal dynamics (ANOVA, ANCOVA)
- GENMOD generalized linear models
- MIXED mixed linear models.

Non-parametric criteria

Below are potential types of comparisons with relevant criteria:

- 1. To evaluate time changes in the parameters compared Friedman test, non-parametric analogue of analysis of variance with repeated measures.
- For frequency analysis of contingency tables 2×2 χ2 (if the frequency under comparison > 5) or exact Fisher's test (if one of the frequencies under comparison < 5).

- 3. Cochran-Mantel-Haenszel test (modified χ^2 test for multiple comparisons) to perform frequency analysis based on independent strata.
- 4. For frequency analysis of data on presence/absence of an event or outcome during repeated measurements (contingency tables with dependent strata) survival analysis.

To perform the above-mentioned nonparametric statistical analysis the following SAS procedures are to be used:

- FREQ Friedman test, χ2 test and/or exact Fisher's test; Cochran-Mantel-Haenszel test
- LIFETEST, PHREG survival analysis
- NPAR1WAY Mann-Whitney U-test

Safety parameters

Adverse events recorded during the study will be grouped into frequency tables by severity, seriousness and relationship with the study drug.

Data presentation

Descriptive statistics will be provided for each study continuous / interval variable. Numerical data will be presented by mean, standard deviation, min and max values. Comparisons suggesting statistical conclusion will have the relevant confidence intervals. Outliers will be analyzed individually. The data will be grouped by visits. The categorical variables will be presented as frequency tables by visits.

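### The primary endpoint is the Day-90 MoCA score, the hypothesis is about change in MoCA, and no primary test is named; one baseline-adjusted ANCOVA settles both

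*Combined protocol and SAP*

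**What the plan says.** Under Endpoints, the single primary endpoint is "Average MoCA score on treatment day 90". The first secondary endpoint is worded as changes in NIHSS, so the plan itself separates level from change.

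Under Evaluation of sample size, item 1.6 defines the first mean in the hypotheses as "change in mean MoCA summary score in MMH-MAP group", and the second likewise for placebo. The code in item 1.7 contains "Samplesize model = twosamplemean (meandiff = 1.3 stddev = 3.0", which is a two-sample comparison without a covariate. The assumptions on expected effects say that the difference between the groups' changes "will be at least 1.3 points with a standard deviation of at least 3.0 points".

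Under Statistical criteria, parametric methods apply when their conditions hold, and methods are "nonparametric in all other cases". Parametric criteria, item 4, says "Generalized Linear Models and/or Mixed Linear Models will be used in case of abnormal data distribution". Item 5 says that "specification of factor and covariance structures of the model will be made using fit-statistics such as AIC". The t-test in item 1 is the paired, within-group one. ANCOVA appears only as an alternative to ANOVA with repeated measures, and no covariate is named. A between-group rank test appears only in the list of SAS procedures ("NPAR1WAY Mann-Whitney U-test").

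The Interim analysis section allows stopping for acceptance or rejection at 30 and 60 patients and names no test. The Schedule of study procedures has MoCA at Visits 1 and 4.

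**The concern.** A confirmatory trial needs one stated quantity and one stated test that decides it. Here the endpoint and the hypothesis name different quantities, and an analyst following the text could defend several tests. Three things are at stake.

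- **Power.** The 80% belongs only to the quantity whose SD is 3.0.
- **The verdict.** An unadjusted Day-90 test and an unadjusted change test on the same data can fall on different sides of the boundary, and the plan does not clearly say which counts.
- **Pre-specification.** Normality checks and AIC let the data influence the choice of test, and nothing in the text fixes that choice across the three looks.

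Separately, an SD of at least 3.0 is the wrong direction for a planning value: any larger SD lowers power.

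**Working it through.** **Inputs from the protocol.** Difference 1.3; SD 3.0; two-sided alpha 0.05; beta 0.2; looks at information 0.15, 0.30 and 1; O'Brien-Fleming shape for alpha and Pocock shape for beta (rho 0.5 and 0 in the code); stopping for both acceptance and rejection; 20% withdrawal.

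**Assumptions not in the documents.** Correlation r between baseline and Day-90 MoCA of 0.3, 0.5 or 0.7; equal SDs at both visits unless stated; normal data; binding acceptance boundaries.

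**1. The plan's own figure.** The code gives rejection at |Z| ≥ 4.84 / 3.42 / 1.87, acceptance at |Z| ≤ 0.02 / 0.51 / 1.87, and a required drift of 3.026. Then n = 2 × (3.0 × 3.026 / 1.3)² = 97.5, so 98 per group, with power 80.2%. For withdrawal, 98 / 0.8 = 122.5, so 123 per group and 246 in total. All stated figures reproduce.

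**2. SD of each candidate analysis.** With S the Day-90 SD:

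- unadjusted Day-90 test: S
- unadjusted change test: S × √(2(1 − r))
- ANCOVA residual: S × √(1 − r²)

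At 98 per group the drift is 1.3 / (SD × √(2/98)) = 9.1 / SD, evaluated against the boundaries above.

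| Reading of 3.0 | Analysis | SD at r = 0.3 / 0.5 / 0.7 | Power |
|---|---|---|---|
| A: SD of change | Day-90 | 2.54 / 3.00 / 3.87 | 90 / 80 / 60% |
| A | Change | 3.00 | 80% throughout |
| A | ANCOVA | 2.42 / 2.60 / 2.77 | 92 / 89 / 85% |
| B: SD of Day-90 score | Day-90 | 3.00 | 80% throughout |
| B | Change | 3.55 / 3.00 / 2.32 | 67 / 80 / 94% |
| B | ANCOVA | 2.86 / 2.60 / 2.14 | 83 / 89 / 96% |

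Under reading A the ANCOVA variance is (1 − r²) / (2(1 − r)) = (1 + r)/2 of the change variance. The size needed for 80% power is therefore 97.5 × 0.65 / 0.75 / 0.85 = 63.4 / 73.1 / 82.9, so 64 / 74 / 83 per group.

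If the Day-90 SD is 0.8 or 1.25 times the baseline SD, ANCOVA power is 80–96% and not below the better unadjusted test.

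**3. Why ANCOVA removes the conflict.** Suppose Day-90 = a + τ × treatment + b × baseline. Subtracting baseline from both sides gives change = a + τ × treatment + (b − 1) × baseline. The estimate of τ, its standard error and its p-value are identical. The Day-90 and change tests fix b at 0 and 1. ANCOVA estimates the b that minimises residual variance, so its large-sample variance is never above either, for any r or SD ratio.

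**4. How often the unadjusted tests disagree.** Normal data were simulated with a true effect of 1.3 and looks at 15, 30 and 98 per group (20,000 trials per setting, Monte Carlo error about 0.3 points). One test rejected and the other did not in about 20 / 24 / 37% of trials under reading A and 27 / 24 / 21% under reading B. Repeat simulations agreed within about 1.5 points. Under the null, each test used alone held type I error at 4.7–5.1%.

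**5. The SD wording.** With an SD of change of 3.25 / 3.5 / 4.0, the drift is 2.80 / 2.60 / 2.28 and the power of the change test is 74 / 68 / 58%.

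**The case against.** The best defence is that the plan has only one hypothesis pair, on change, ties the sample size to the primary criterion, and codes one two-sample-mean model for all three stages. Read together, these suggest an unadjusted comparison of mean change, and the endpoint line is loose wording. On that view 3.0 is the SD of change, and reading B has little support.

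Much of this is fair. Change is the more natural reading of the SD. Under randomization the expected group difference is also the same for level and change, so the target is not in dispute. What differs is the estimator, its variance and its power. Disagreement between tests means significant against not significant, not effects in opposite directions. No inflation of type I error from choosing among tests was computed. The generalized models can be read as a middle step before rank methods rather than as a contradiction. The wording of at least 3.0 may be a translation slip. The document also calls itself a protocol summary.

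The defence still has to infer the primary test from a sample-size code, against the stated endpoint and alongside a list that invites selection by normality and AIC. A named t-test on change would also remove the ambiguity, but ANCOVA does so with power at least as high in large samples. Its gain depends on r: it vanishes against the Day-90 test as r nears 0 and against the change test as r nears 1. The price is one degree of freedom. In a fixed-sample calculation at r = 0, power falls from 85.5% to 85.3% at 98 per group, and by about 0.6 points at 15 or 30 per group.

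**Conclusion.** The concern holds. The endpoint and the hypothesis name different quantities, and no test is assigned to the primary endpoint. The sample size is sound on its own inputs; the fault lies in the specification of the analysis. Leaving the choice open puts the power of the unadjusted tests anywhere from 60% to 90% under reading A, or 67% to 94% under reading B. It also leaves the verdict dependent on that choice in about one trial in five to more than one in three. These sizes rest on the assumed correlations of 0.3–0.7 and equal SDs at both visits. The textual conflict and the equivalence of level and change under ANCOVA need no such assumption.

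**What to change.** Before any comparison by treatment group, amend the protocol and SAP as follows.

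- Name one primary analysis and use it unchanged at the looks with 30, 60 and 196 patients: a linear model of Day-90 MoCA on treatment with Visit 1 MoCA as covariate, reporting the adjusted mean difference, its confidence interval and p-value.
- Reword the primary endpoint and the hypotheses so that both refer to that adjusted difference.
- For this endpoint, move normality-driven switching, AIC selection and rank-based methods (Mann-Whitney, rank ANCOVA) to sensitivity analyses.
- State whether 3.0 is the SD of change or of the Day-90 score, and word it as no more than 3.0.

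The cost is a wording amendment and one degree of freedom. Baseline MoCA is already collected, so no patients, visits or procedures are added. The amendment does not settle the handling of missing Day-90 MoCA, which needs its own rule.

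### The day-90 mRS 0-1 endpoint has no named test and no commitment to adjust for baseline mRS (2 versus 3); a stratified CMH analysis should be pre-specified, for a modest and assumption-dependent gain

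*Combined protocol and SAP*

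**What the plan says.** Under Secondary endpoints, item 2 is "Percentage of patients with no major disability (mRs 0-1) after 90-day therapy". Inclusion criterion 6 is "Disability mRs score 2-3". In the Schedule of study procedures, the row "Filling mRs scale" is marked at Visit 1 and Visit 4, so baseline mRS is known for every randomised patient.

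The section Non-parametric criteria opens with "Below are potential types of comparisons with relevant criteria". Item 2 of that list is introduced by "For frequency analysis of contingency tables 2×2" and gives chi-square, or "exact Fisher's test (if one of the frequencies under comparison < 5"). Item 3 is the CMH test, "to perform frequency analysis based on independent strata". No stratifying variable is named, and neither item is linked to the mRS endpoint. The section Parametric criteria also lists GENMOD, which could fit a baseline-adjusted binary model. Under Evaluation of sample size, "statistical criteria of intergroup comparisons are two-sided, unless otherwise stated".

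The documents describe no stratified randomisation, give no expected mRS response rates or baseline mRS mix, and make no power claim for this endpoint.

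**The concern.** The entry criterion and the response cut-off together fix the distance each patient must travel: one grade from mRS 2, two grades from mRS 3. That is good reason to expect different response rates at the two levels, whatever the treatment does. An analysis that ignores the split has two weaknesses.

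- **Precision.** The variation between baseline levels stays in the error term.
- **Chance imbalance.** No stratified allocation is described, so the share of patients at mRS 2 can differ between arms by chance. That difference then passes into the unadjusted comparison.

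Because the list of tests is not mapped to endpoints, the choice between an unadjusted and a stratified analysis also stays open until the data are seen.

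**Working it through.** **The plan's own figure.** The only sample size stated is for the primary MoCA endpoint. Recomputing the three-stage design (information 0.15, 0.30, 1; difference 1.3; SD 3.0; alpha 0.05; beta 0.2) gives 97.5, so 98 per arm. Then 98 / 0.8 = 122.5, so 123 per arm and 246 in total. Both agree with the plan. There is no mRS figure to reproduce.

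**Inputs for the mRS endpoint.** From the documents: 98 completers per arm, 1:1 allocation, two-sided testing, alpha 0.05. Assumed: control response at each baseline level, the share of patients at mRS 2, and a common odds ratio (OR) across levels.

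**One case by hand.** Take control response 50% at mRS 2 and 20% at mRS 3, half the patients at each level, OR 2.

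1. Treated response, p × OR / (1 − p + p × OR): 1.0/1.5 = 66.7% at mRS 2; 0.4/1.2 = 33.3% at mRS 3.
2. Overall: 35% versus 50%, a difference of 0.15, with pooled proportion 0.425.
3. Unadjusted: variance 0.425 × 0.575 = 0.2444; z = 0.15 / √(2 × 0.2444/98) = 2.124; power = Φ(2.124 − 1.96) = 56.5%.
4. Stratified: within-level variances are 0.5833 × 0.4167 = 0.2431 and 0.2667 × 0.7333 = 0.1956, mean 0.2193; z = 0.15 / √(2 × 0.2193/98) = 2.242; power = Φ(2.242 − 1.96) = 61.1%.
5. Ratio of variances: 0.2444/0.2193 = 1.11, equivalent to about 11% more patients.

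**Other cases.** All are at 98 per arm. The simulations use unstratified 1:1 allocation, so chance differences in the mix are included.

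| Control response, mRS 2 / mRS 3 | Share at mRS 2 | Effect | Unadjusted to CMH (or change in points) |
|---|---|---|---|
| 40% / 40% | 50% | OR 2 | 68.3% to 67.4% (simulated) |
| 50% / 40% | 50% | OR 2 | 67.4% to 66.8% (simulated) |
| 40% / 30% | 50% | OR 2 | 66.0% to 65.8% (simulated) |
| 50% / 30% | 50% | OR 2 | 64.8% to 65.3% (simulated) |
| 40% / 20% | 50% | OR 2 | 59.6% to 61.8% (formula); 59.2% to 61.9% (simulated) |
| 50% / 20% | 50% | OR 2 | 56.5% to 61.1% (formula); 57.1% to 61.2% (simulated) |
| 50% / 20% | 10% | OR 2 | 55.8% to 57.2% |
| 50% / 20% | 90% | OR 2 | 64.2% to 64.9% |
| 60% / 15% | 50% | OR 2 | 45.2% to 55.1% (formula); 46.0% to 55.2% (simulated) |
| 60% / 30% | 25–75% | OR 1.8, or OR giving about 80% unadjusted power | +1.7 to +2.9 (simulated) |
| 70% / 20% | 25–75% | same | +7.2 to +9.0 (simulated) |

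In the simulations with 25–75% of patients at mRS 2, type I error was 4.8–5.4% for the unadjusted test and 4.9–5.2% for CMH.

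**Chance imbalance.** With half the patients at mRS 2, the SD of the between-arm difference in that share is √(2 × 0.25/98) = 0.0714. A 1.96-SD imbalance is 0.14. It moves the unadjusted difference by 0.14 × gap: 1.4 points at a 10-point gap, 4.2 at 30 and 7.0 at 50. In the worked case the true difference is 15 points.

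**The case against.** The strongest reply is that the plan has made no wrong choice here. A reader might infer that it assigns a plain chi-square or Fisher test to this endpoint. The documents do not support that: the list is one of possible methods, CMH stands beside chi-square in it, and GENMOD is available too. What stands is the gap itself, since neither the test nor the stratum is fixed.

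A reader might also infer that stratifying is certain to add power at no cost. That does not follow either. The number of grades to improve is set by definition, but how strongly an mRS score within 72 hours of onset predicts day-90 response is an empirical matter, and the documents give no rates. With a gap of 10 points or less between the levels, the gain is nil or slightly negative. With nearly all patients at one level, it shrinks to about 1 point even at a 30-point gap.

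Finally, the unadjusted test is valid under randomisation. That is correct. The imbalance argument concerns the precision of the estimate in the trial actually run, not the error rate over repeated trials.

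These points limit the size of the benefit. They do not remove the reason to act: the largest power loss found is about 1 point, the possible gain is several points, and the data are already collected.

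**Conclusion.** The concern holds as a minor, inexpensive improvement to a secondary analysis. The mRS 0-1 analysis is not specified, its default reading ignores a baseline value that is likely to be prognostic, and the listed CMH test lacks a stratum.

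At 98 per arm, and depending on response rates and a baseline mix that the documents do not state, stratifying by baseline mRS changes power by about -1 to +10 points:

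- nil or slightly negative at a gap of 10 points or less in control response between mRS 2 and mRS 3;
- about 0 to 3 points at a 20-point gap;
- about 2 to 4 points at a 30-point gap with a balanced mix;
- about 7 to 10 points at a 45- to 50-point gap;
- less if nearly all patients enter at one level.

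These figures assume a common odds ratio at both levels. The benefit is precision and protection against chance imbalance; type I error is not at issue. The primary MoCA analysis and the sample size are unaffected.

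**What to change.** Keep the endpoint as defined and add one sentence to the statistical section: mRS 0-1 at day 90 is compared between arms by the CMH test stratified by baseline mRS (2 versus 3), with a stratified odds ratio or risk difference (state in advance which) and its confidence interval. A logistic model with baseline mRS as a covariate would be an acceptable alternative, provided that it is the one named.

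The cost is that sentence. CMH and PROC FREQ are already listed, baseline mRS is already recorded at Visit 1, and eligibility, visits and sample size do not change. The statistical price is a power loss of at most about 1 point if baseline mRS turns out not to be prognostic.
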